4.1.1. Inclusion criteria

- Children (boys and girls) between 24 and 48 months.
- Children from Birmingham and its surrounding areas.
- Monolingual English native speakers
- Children with a moderate or severe language delay, as diagnosed by a Speech and Language Therapist of the Birmingham Community Healthcare NHS Foundation Trust.

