4.1.3. Participant identification and recruitment

We will recruit children via the Speech and Language Therapy Services from the Birmingham Community Healthcare NHS Foundation Trust. Parents/guardians of children that have been referred to these services are invited to attend an individual screening session. In this session, children are evaluated and divided into three categories: children with a mild language delay, children with a moderate delay, and children with a severe delay. Only children with a severe language delay are invited to take part in a subsequent intervention programme run by the NHS services, while it could currently take up to a year between the initial assessment and the start of the intervention. Parents/guardians of children with mild or moderate language delays are provided with guidance on how to support their child's language development and to contact the services again if the child seems to continue to lag behind their peers in their language development.

Parents/guardians of children that fulfil our inclusion exclusion criteria above (i.e. have either a moderate or severe language delay among other criteria) will be provided by the speech and language therapist with a brochure/leaflet (Appendix 1.1) about the present study at the end of the

initial assessment. The therapist will inform them that they can contact us in order to see whether the child might be able to participate in our study. In case of children with a diagnosis of severe language delay, the intervention will take place during the time that they wait for the start of their intervention conducted by the NHS services. They will be informed by the therapist and through the study brochure that their participation will not affect the services provided to them by the Birmingham Community Healthcare NHS Foundation Trust and that they will still receive an evaluation/intervention appointment with them in the future as planned.

The brochure (see Appendix 1.1) will contain information about the study, and the Chief Investigator/Researcher's contact details. If parents/guardians are interested, they can contact the Chief Investigator or researcher. If the children meet the inclusion and exclusion criteria and if capacity allows, they will be invited to take part in the present study at the Infant and Child Lab at the University of Birmingham.

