4.3. Tests and procedure of intervention programme

4.3.1. Vocabulary and developmental assessments. At session 1, parents/guardians will fill in a socioeconomic and general development questionnaire (see Appendix 1.5). The

information provided in this questionnaire will double-check the inclusion/exclusion criteria. It will also be used to check whether the intervention was only successful in a sub-group of the infants (e.g. those without a family history of language problems). In the first and last session, parents/guardians will also be asked to fill in the UK-CDI Words and Gestures questionnaire, a vocabulary checklist of words and phrases that infants might know and use (Alcock, Meints, & Rowland, 2017; see Appendix 1.4). This will allow us to compare language development during the intervention programme between the two intervention groups.

4.3.2. Initial cognitive assessments: The initial cognitive assessments will be presented during the first two sessions. During week 1, infants will be assessed with a shape sorting task and an attention task. The sorting task will last no more than 5 minutes and will be used to assess if before the training programme, infants are sensitive to the shape of objects and can group objects by shape. Infants will be presented with 16 novel objects differing in shape, colour and texture and asked to sort them into groups. How to sort (namely by shape) will be shown to them with the means of examples. The attention task will last 3 minutes and will assess infants' joint and sustained attention. This will be achieved by monitoring their eye movements during the presentation of five short video clips (35 seconds each) of a person looking at and moving unusual novel objects. For this task, participants will sit on their parent/guardian's lap in front of a computer screen. Eye movement will be monitored with a remote eye tracker (see Figure 2). The parent will wear blacked-out glasses so that their behaviour cannot affect the infants' eye gazes.

At week 2, infants' visual spatial abilities and working memory will be assessed using the Wechsler Preschool & Primary Scale of Intelligence - Fourth UK Edition (WPPSI-IV UK). This test will last about 20 minutes and will be used to rule out any potential cognitive delay.

Figure 2. Attention task. Infants will watch five short videos and eye movements will be monitored with a remote eye tracker.

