6.3.1 Summary of baseline data

From the total number of assessments and tasks, results from five of them will be used as baseline data or descriptive statistics. These five assessments are: Vocabulary checklist, Socioeconomic and general development questionnaire, attention task, sorting task, initial working memory assessment, and initial visual spatial abilities assessment. The description of the variables analysed on each assessment and how they will be reported is as follows.

- A. Vocabulary assessment: Parents will fill out this checklist before (and after) the intervention and the total number of words that the infant understands and the total number of words they

produce will be registered as continuous variables and will be considered as the baseline language ability before the intervention programme.

- B. Socioeconomic and general development questionnaire: This questionnaire will provide information regarding general child development, language delay family history, and family status. A number of different types of variables will be collected: nominal variables (e.g. occupation) and ordinal variables (e.g. infant's order of birth). These variables will be used for descriptive statistics. They are potentially interesting as predictor variables, but the sample size is likely too small to draw any strong conclusions.
- C. Attention measure: With this measure, we will assess the fixation duration (number of milliseconds an infant looks) towards a novel object that is moved. The object will be moved for 25 seconds (25000 ms) and the infant's total looking time towards the screen will be registered. This variable will be registered as a continuous variable and used as a predictor of the primary outcome measures.
- D. Sorting task: This will be registered as a categorical variable. Infants will sort objects and depending on their sorting tendency they will be assigned to one of four categories: preference for shape, preference for colour, preference for texture, no preference. This variable will be used as a predictor of the primary outcome measures.

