6.3.2 Primary outcome analysis

During weeks 8 and 9 of the study infants will be assessed with two forced choice tasks where they will have to extend object names to new exemplars based on visual commonalities. We will assess the statistical difference between the response pattern and chance (using t-tests). This will show whether infants have learned to extend object names by shape similarities. The factors that predict the number of noun extensions based on shape as well as vocabulary growth will be assessed using mixed effect model analyses. The most important factors tested in the models will be the number of words known before the intervention, the intervention type (shape training vs specific word training), attention measures (pre-test and attention during training), and sorting task measure. The outcome of these analyses will show whether the shape bias intervention has led to a larger vocabulary growth than the specific word intervention (as a control intervention). It will also assess the role of attention in word learning and whether only infants that pay attention to novel items

presented to them or infants that are sensitive to shape similarities between objects can acquire a shape bias. Only data of infants that complete the intervention will be analysed.

Regarding the follow up study, infants' vocabulary and cognitive abilities will be assessed. This with the aim of analysing if there are any long-term effects of each intervention and infants continue learning words and potentially "catching up", or if the intervention programmes are only beneficial while they are being implemented. The cognitive assessments will be used to assess whether the intervention has an effect on visual spatial skills and working memory. In both cases, it will be done by comparing the infants results to the standardized mean of UK infant population. Similarly, infant's result in the follow up language assessment will be compared to the standarized mean of UK infant population.

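### Section 6.3.2 does not name age as a factor in the arm-contrast models despite a 24–48 month entry range and a raw word-count outcome, and it lists attention during training, a post-randomisation measure, among their factors

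*Combined protocol and SAP*

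**What the plan says.** All references are to the combined protocol and SAP.

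- **Model factors (6.3.2).** Mixed-effects models are planned for the number of shape-based extensions and for vocabulary growth. "The most important factors tested in the models will be the number of words known before the intervention"; the list continues with intervention type, then "attention measures (pre-test and attention during training), and sorting task measure". Section 6.3.3 names attention and sorting again for the secondary objectives. Neither age nor severity of delay appears anywhere in 6.3.
- **Age (4.1.1).** "Children (boys and girls) between 24 and 48 months".
- **Severity (4.1.1, 4.1.3).** Entry requires "Children with a moderate or severe language delay, as diagnosed by a Speech and Language Therapist". At the NHS screening session, 4.1.3 has each child graded into one of these groups: "children with a mild language delay, children with a moderate delay, and children with a severe delay".
- **Outcome scale (6.3.1 A).** Vocabulary is recorded as counts of words understood and words produced. No age norming is stated, whereas the cognitive and follow-up results are to be set against UK population means.
- **Allocation (4.2).** Random to two groups, with no ratio, blocking, stratification or minimisation described.
- **Baseline variables (6.3.1).** Neither age nor severity is listed. Of the socioeconomic and development questionnaire variables the plan says "They are potentially interesting as predictor variables, but the sample size is likely too small to draw any strong conclusions". Section 4.3.1 adds that the "information provided in this questionnaire will double-check the inclusion/exclusion criteria".

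**The concern.** The oldest eligible child is twice the age of the youngest, and the protocol's own introduction describes both vocabulary and the shape bias as changing with age. Two children with the same session-1 word count but very different ages may have different expected growth over nine weeks. As written, age is handled neither by the allocation nor by a named covariate.

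Meanwhile the named list gives up to five degrees of freedom to terms that serve Objectives D and E: two attention measures and a four-category sorting variable. One of these, attention during training, is observed after randomisation.

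At stake are the precision of the Objective B arm contrast with about 12 children per arm, its sensitivity to a chance age difference, and its interpretation if part of the treatment effect is adjusted away. An open list also leaves covariates to be chosen after the data are seen.

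**Working it through.** **Inputs.** N = 24 completers, with 30 as the recruitment target (6.1). Equal allocation is assumed, because no ratio is given. One outcome value per child is assumed, analysed by ANCOVA. The documents give no standard deviation and no correlation of age or severity with growth. The share r² of the remaining variance that the added covariates explain is therefore an assumption, shown over a range.

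**The plan's own figure.** The plan states nothing on precision that could be reproduced. The figure of 24 is used only as N. The test, number of measurements and correlation behind it are not stated, so it can be neither confirmed nor refuted, and nothing below depends on it.

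**Formula.** With k covariate degrees of freedom besides arm, in residual SD units:

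Var(arm effect) = (4/N) × (N−3)/(N−3−k) × (1−r²)

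**1. Add age alone to arm + baseline words (k from 1 to 2), N = 24.** SE ratio = √[(20/19)(1−r²)].

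| r² | SE ratio |
|---|---|
| 0 | √1.053 = 1.03 |
| 0.10 | √0.947 = 0.97 |
| 0.20 | √0.842 = 0.92 |

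Break-even: r² = 1 − 19/20 = 0.05. At N = 30 it is 1 − 25/26 = 0.04.

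**2. Add age and severity together (k from 1 to 3), N = 24.** SE ratio = √[(20/18)(1−r²)]: 1.05 at r² = 0, 1.00 at 0.10 and 0.94 at 0.20. Break-even: 1 − 18/20 = 0.10. If both are added on top of every listed factor (k from 6 to 8), break-even is 1 − 13/15 = 0.13.

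**3. Replace attention and sorting rather than add to them.** The listed factors use k = 1 (words) + 2 (attention) + 3 (sorting) = 6. Words + age + severity use k = 3. If the two sets explain equal variance:

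- N = 24: √[(21/18)/(21/15)] = √(15/18) = 0.91
- N = 30: √[(27/24)/(27/21)] = √(21/24) = 0.94
- N = 24 without severity (k = 2): √(15/19) = 0.89

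At N = 24 with k = 3, the exchange breaks even if residual variance rises by a factor of 18/15 = 1.20, that is by 20%.

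**4. Chance imbalance.** If ages are uniform on 24–48 months, their SD is 24/√12 = 6.93 months. The SD of the difference in means at 12 per arm is 6.93 × √(2/12) = 2.83. By simulation, mean ages differ by 3 months or more with probability 0.29 (0.24 at 15 per arm). For severity, if 8 or 12 of 24 children are severe, the hypergeometric probability that the arms differ by 4 or more severe children is 0.19 or 0.22.

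**5. Attention during training.** By 4.3.3, one arm handles novel objects and the other real common objects. Objective E (3.4) defines the measure as attention to novel objects during the intervention. It is therefore taken after allocation, under conditions that the allocation sets. Conditioning the arm contrast on it can remove part of the effect being estimated.

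**The case against.** A reader might infer that the plan excludes age and severity. It does not: 6.3.2 names the most important factors, which leaves the list open.

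A reader might also infer that both variables are already recorded. Age must be known to check eligibility. For severity the documents are weaker. NHS therapists assign the grade, families then approach the study, and eligibility needs only mild separated from the rest. No passage shows that moderate versus severe reaches the study data, and the questionnaire itself is in an appendix outside the text.

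Nor do the documents show that the planned analysis is necessarily noisier than it need be. Baseline words are already in the model and may carry much of the age and severity signal. Below the break-even shares, adjustment costs precision. Large gains need shares such as 40%, which nothing in the documents supports.

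Chance imbalance under randomisation is not bias, and the standard error allows for it. The raw-count argument also applies to Objective B, not directly to Objective A. The plan deliberately makes sorting and pre-test attention predictors of the primary outcomes (6.3.1), so dropping them could lose precision. Finally, the effect on power is small: for an assumed effect of 0.5 residual SD at N = 24, power is 0.207 with baseline words alone, and with age and severity added it is 0.190 at r² = 0 and 0.226 at r² = 0.20.

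These points limit the size of the concern but do not remove it. Age alone has a low break-even and a small worst-case cost. The small-sample remark in 6.3.1 concerns drawing conclusions about questionnaire predictors, not baseline adjustment of the arm effect. The objection to a post-randomisation covariate does not depend on any assumed correlation.

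**Conclusion.** The point holds in a limited form. Section 6.3.2 should say whether age is a covariate. With this entry range, an unnormed word total and no stated stratification, including it is the better default. At N = 24 the standard error of the arm effect changes by about +3% to −8% as the share of remaining variance explained by age goes from 0 to 20%, with break-even near 5%. Age and severity together need about 10%, so the case for severity is weaker and depends on the grade being available.

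Attention during training should leave the arm-contrast model whatever is decided about age. Going from 6 to 3 covariate degrees of freedom multiplies the standard error by about 0.91, but only if the two covariate sets explain equal variance.

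All of this rests on assumed r², equal allocation and one value per child. The change improves the specification and will not by itself give Objective B adequate power.

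**What to change.** - **6.3.2:** prespecify the Objective B arm-contrast model as arm, session-1 words and age in months. Use the same covariates for the arm comparison of shape-based extensions under Objective A.
- **Severity:** add moderate versus severe only if the screening grade can be obtained by the study.
- **6.3.1:** list age in months, and severity if available, as baseline variables.
- **Attention during training:** remove it from the arm-contrast models.
- **6.3.3:** estimate the attention and sorting terms in separate models for Objectives D and E.

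**Cost:** a wording change for age. Severity may also require arranging for the grade to be passed on. Statistically, the cost is one or two degrees of freedom, plus some loss of precision if sorting or pre-test attention proves strongly prognostic.

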3.3. Primary outcome measures

Objective A), i.e. whether children have learned a shape bias, will be assessed by means of a noun extension test with novel names and objects never heard and seen before by the infants at the end of the intervention programme.

Objective B), i.e. whether the intervention programme benefits infants' general vocabulary development, will be assessed with a vocabulary checklist filled in by the parents/guardians before and after both types of intervention. We will compare the vocabulary growth in the group of children that took part in the shape bias intervention programme with that of the group of children that took part in the 'specific word' intervention. A significant larger increase in the shape bias intervention compared to the 'specific word' intervention will provide information regarding the success or efficacy of the shape bias intervention.

Objective C), i.e. whether the shape bias intervention has a "long-term" effect on language development and cognitive abilities. Receptive and expressive language, and cognitive abilities, such as visual spatial skills and working memory, will be assessed at one year after the end of the intervention programme.

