3.4. Secondary outcome measures

Objective D), i.e. whether children are more receptive to the shape bias intervention if they are sensitive to shape similarities, will be assessed by relating children's ability to sort objects by shape before the intervention and their ability to extend object labels by shape after the intervention.

Objective E), i.e. whether children' are more receptive to the shape bias intervention if they can sustain their attention to novel objects, will be assessed by relating children's sustained attention during the presentation of a video showing a person presenting and moving novel objects before the intervention, their attention to the novel objects during the intervention, and their ability to extend object labels by shape after the intervention.

4. Method

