4.2. Study design

Infants will be randomly allocated to one of two groups: shape training group or specific word training group. Over a series of 9 weekly sessions, all infants will be assessed on different tasks that can be divided into 5 stages: Vocabulary and developmental assessments, initial cognitive assessments, training sessions, first-order generalization test, higher-order generalization test. Depending on the group that the children will be in, they will receive either a shape training or a specific word training. Other assessments (initial assessments, cognitive assessments, first-order generalization test and higher-order generalization test) will be identical across the groups. Additionally, a follow up study will be conducted after one year of completion of the intervention programme. A table describing the intervention procedure is provided in Figure 1. Details of the tasks are given below.

[figure not shown]

Figure 1. Timeline of intervention programmes.

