4.3.3. Training sessions

4.3.3.1. Shape training: During the first seven weeks, infants will be presented with four novel words paired with four novel sets of objects (total duration 15 minutes). Each set will consist of two exemplars with the same shape but with different colours and textures. Each set will be presented with sentences such as “*Look! It is a kiv. Do you want to play with the kiv?, Let’s play with the kiv*”. Half way through the presentation of the exemplars, the researcher will bring out a third contrasting object. This contrasting object will be presented with the sentence “*Oh no, this is not a kiv*” and will be taken away immediately. The other three sets of novel exemplars will be presented in the same manner.

4.3.3.2. ‘Specific word’ training: This training will resemble a typical word learning intervention. During the first seven weeks infants will be introduced to 28 real common objects and their names (e.g. biscuit, trousers, slide), randomly divided into 7 sets of four words. During each session, infants will be presented with one of the sets and each session will have a total duration of 15 minutes. The target words have been selected from the Wordbank database, an open database that lists the proportion of children that know a specific word at a specific age. Twenty-eight words that 80% of the total child population at 25 months know were randomly selected as target words. Each session will consist of a 15 min play session in which each object name will be presented at least 10 times and each object name will be mentioned at least 10 times. Additionally, techniques such as focused stimulation and modelling target words, which have proved to be useful for word learning, will be used.

4.3.4. First-order generalization: At week 8 infants in both groups will be assessed as to whether they have learned that objects that have the same shape share the same name. They will be presented with each exemplar used during the training sessions accompanied by three novel toys. These three objects will share only one visual property with the training objects (colour, shape or texture). The three objects will be placed on a table and the researcher will say “*This is a kiv, Can you show me the other kiv?*” while he/she shows the infant one of the exemplars used during the 7 training weeks. All infants will be tested on each trained object with the same procedure. This test will last 8 minutes.

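### Section 6.3.2 lists attention during training, a post-randomisation variable, in the models meant to show the arm difference, and no between-arm model without it is named

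*Combined protocol and SAP*

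**What the plan says.** All references are to the combined protocol and SAP. Section 3.3 frames Objective B as a contrast between groups: "We will compare the vocabulary growth in the group of children that took part in the shape bias intervention programme" with growth in the specific word group. Section 4.3.1 says of the vocabulary checklist, completed at the first and last sessions: "This will allow us to compare language development during the intervention programme between the two intervention groups". Neither section gives a model.

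Section 6.3.2 is the only place that gives a method. It applies mixed models to two outcomes, shape-based noun extensions and vocabulary growth. The factors it singles out are words known at baseline and "the intervention type (shape training vs specific word training), attention measures (pre-test and attention during training), and sorting task measure". It then states: "The outcome of these analyses will show whether the shape bias intervention has led to a larger vocabulary growth than the specific word intervention". The same models have a further purpose: "It will also assess the role of attention in word learning". Section 6.3.3 refers back to the same model for the secondary outcomes.

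On timing, section 4.2 says "Infants will be randomly allocated to one of two groups". Training then fills weeks 1 to 7 with different material in each arm. In the shape arm "infants will be presented with four novel words paired with four novel sets of objects" (section 4.3.3.1), while the other arm plays with 28 everyday objects (section 4.3.3.2). For Objective E, section 3.4 describes the variable as "their attention to the novel objects during the intervention". Section 6.3.1, item C, defines only the pre-test video measure of attention.

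**The concern.** Randomisation makes the two arms comparable on everything fixed before training. It does not do so for a variable that training itself can change. Novel objects and familiar toys may hold a child's attention differently, so allocation could plausibly move attention during training, and attention could in turn relate to word learning. A model containing both intervention type and training attention compares children at equal levels of attention. That is a different question from whether one type of training produced more vocabulary growth than the other.

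At stake is the contrast that decides Objective B, and also the between-arm contrast for noun extension. The shift could hide a benefit or suggest one that is absent. The t-tests against chance in section 6.3.2 contain no covariates and are unaffected.

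**Working it through.** **Is a model without the variable named?** Sections 3.3 and 4.3.1 state a comparison but no model. Section 6.3.2 gives the models and lists the variable. Section 6.3.3 points back to them. So none is named.

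**Is the variable defined in both arms?** Section 3.4 speaks of novel objects, and only the shape arm trains on these. What would be scored in the specific word arm is not stated. There are two cases.

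*Case 1: scored only in the shape arm.* The variable has no value in the other arm, so it cannot enter a two-arm model at all.

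*Case 2: scored in both arms.* Let T be the arm (1 = shape), M attention during training and Y the outcome, in a linear model without interaction:

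- M = δ·T + error
- Y = (τ − δβ)·T + β·M + error

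Here τ is the arm difference, δ the arm difference in attention and β the attention slope. The coefficient of T without M is τ. With M it is τ − δβ. The two agree only if δ or β is zero.

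The slope need not be causal. Suppose neither T nor M affects Y, but a shared cause loads 0.6 on both M and Y (both assumed). The fitted slope is then 0.6 × 0.6 = 0.36. With δ = 0.8 the T coefficient is −0.8 × 0.36 = −0.29, and simulation at 12 per arm gave −0.29 with 10% rejection.

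**Inputs.** The plan gives 24 completers (section 6.1), so 12 per arm if allocation is 1:1; the ratio is not stated. The documents give no δ, β or τ, so all three are assumed, with τ = 0.5 SD. This point disputes no figure in the plan.

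**Simulation.** Ordinary least squares stood in for the mixed model, with 20,000 trials per cell. Ranges cover four set-ups: outcome within-arm SD 1 or residual SD 1, each with and without baseline covariates.

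| Case | δ, β | Adjusted term, τ − δβ | Null rejection | Chance of significance when τ = 0.5 |
|---|---|---|---|---|
| Moderate | ±0.3, 0.3 | 0.5 ∓ 0.09 = 0.41 or 0.59 | 5–6% | 14–16% or 23–29% |
| Middle | ±0.5, 0.5 | 0.5 ∓ 0.25 = 0.25 or 0.75 | 8–10% | 8–10% or 33–48% |
| Large | ±0.8, 0.5 | 0.5 ∓ 0.40 = 0.10 or 0.90 | 12–17% | 5–6% or 41–59% |
| No attention difference | 0, 0.5 | 0.50 | 5% | – |
| No slope | 0.8, 0 | 0.50 | 5% | – |
| Variable left out | any | 0.50 | 5% | 17–22% |

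The moderate shift of 0.09 compares with a standard error of 0.40–0.45. The large shift of 0.40 is about one standard error (0.39–0.50). If all 30 children complete (15 per arm), null rejection in the large case is about 14–20% over the four set-ups.

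**The case against.** The strongest reply is that section 6.3.2 does not commit to any one model. It speaks of models in the plural, of factors to be tested, and of the most important ones only. The same models serve Objectives B, D and E. Section 3.4 ties attention during the intervention to shape extension, not to vocabulary growth. An analyst could reasonably fit arm and baseline words for Objective B and keep training attention for Objective E. This stands as far as it goes: a reader might infer that the plan requires the Objective B contrast to be adjusted for training attention, and the text does not support that. But nothing in the plan excludes it either, and the sentence that promises the Objective B answer refers to these analyses without distinction.

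The reply is also right that the formula is exact only for a linear model without interaction. Section 6.3.2 asks whether only attentive infants acquire a shape bias, which suggests an arm-by-attention interaction. Noun extension is a number of forced choices and might be modelled with a logit link. In either case the identity is not exact, but the arm term still no longer estimates the plain arm difference. The simulation covers a continuous outcome only.

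Finally, the size is wholly assumed. In the moderate case the shift is small beside the sampling error, and under these assumptions power is only 17–22% without the variable, so imprecision dominates in that case. That is a fair limit on the size of the point. It is not a reason to leave the model open.

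**Conclusion.** The point holds in a limited form. The plan lists a variable that arises after randomisation among the factors of the models that are to show the arm difference, and names no between-arm model without it. If the variable is scored in both arms and entered, the intervention term need not equal the difference due to training type. If it is scored only in the shape arm, it cannot be entered in a two-arm model.

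Under the assumed inputs the shift runs from none to 0.40 SD, in either direction. A reader might take the large case as the expected bias, or infer that the shape arm will be favoured. The documents support neither, since they give no attention difference and no slope. Nor should one infer that removing the variable recovers the full effect of allocation. Sections 6.3 and 6.3.2 restrict the analysis to children who complete the intervention, so the result is the arm contrast among completers. That restriction is a separate issue.

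The matter should be settled before analysis. Confidence is moderate, because the list leaves room for a sound model.

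**What to change.** State in section 6.3.2 that the between-arm effects on vocabulary growth and on noun extension are judged in a model with intervention type and only covariates measured before training: words known, pre-test attention and the sorting task. Use attention during training only in a separate analysis for Objective E and the role of attention in word learning, within the shape arm if it is scored only there. Define how it is measured and on which objects it is scored in each arm.

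The cost is one sentence, one definition and one extra model, with no new data or participants. If attention predicts growth but does not differ by arm, leaving it out loses a little precision: a standard error of about 0.40 instead of 0.36 at a slope of 0.5 (12 per arm, outcome SD 1, no baseline covariates). If attention differs by 0.8 SD but has no slope, leaving it out gains precision (0.40 instead of 0.45).
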